5.3. Method of Assignment to Treatment

Patients who meet all Visit 1 and Visit 2 eligibility criteria for enrollment will be randomized at Visit 2 (Week 0) in a 1:1 ratio to open-label treatment with ixekizumab or adalimumab at Week 0 (Visit 2). Assignment to treatment groups will be determined by a computer-generated random sequence using an interactive web-response system (IWRS). The IWRS will be used to assign investigational product to each patient. Site personnel will confirm that they have located the correct investigational product by entering a confirmation number found on the investigational product into the IWRS. The randomization will be stratified by concomitant csDMARD use at baseline (Yes, No) and moderate-to-severe plaque psoriasis involvement (Yes, No).

6. A Priori Statistical Methods

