6.2. Analysis Methods

6.2.1. Categorical

Unless specified otherwise, the primary analysis method for the binary categorical efficacy and health outcome variables will be a logistic regression model with treatment, concomitant csDMARD use at baseline, and moderate-to-severe plaque psoriasis involvement as factors. The odds ratios and the corresponding 95% CIs will be reported. Fisher's exact test will be used as the secondary analysis method.

For ordinal categorical variables, a logistic regression model using cumulative logits will be used.

Treatment differences (Absolute Risk Reductions [ARR]), Relative Risks (RR), Numbers Needed to Treat (NNT) estimates, and their corresponding 95% CIs (using normal approximation) will also be reported. See [Appendix 1](#) for more details.

The statistical methodology for assessing noninferiority of ixekizumab to adalimumab for ACR50 is described in [Section 6.7](#).

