6.2.2. Continuous Endpoints

Unless specified otherwise, the primary analysis method for all continuous efficacy and health outcome variables will be a MMRM analysis. The model will include treatment group, concomitant csDMARD use at baseline, moderate-to-severe plaque psoriasis involvement, visit-as-fixed factors, baseline value as covariate and baseline-by-visit and treatment-by-visit interaction terms. The MMRM analyses will be conducted using a restricted maximum likelihood (REML)-based repeated measures approach. The covariance structure to model the within-patient errors will be unstructured. If the unstructured covariance matrix results in a lack

of convergence, the heterogeneous Toeplitz covariance structure, followed by the heterogeneous autoregressive covariance structure, followed by the compound symmetry structure will be used. The first structure to yield convergence will be used for inference. The Newton-Raphson with ridging optimization technique will be used to aid with convergence. The Kenward-Roger approximation will be used to estimate the denominator degrees of freedom and adjust standard errors. Type III tests for the least squares (LS)Means will be used for the statistical comparison; the 95% CI will also be reported.

An analysis of covariance (ANCOVA) model and mBOCF imputation method as detailed in Section 6.4.2 will be used as the secondary analysis method for treatment comparisons on continuous efficacy and health outcome variables. The ANCOVA model will include treatment, concomitant csDMARD use at baseline, moderate-to-severe plaque psoriasis involvement, and baseline value in the model. Type III sums of squares for the LSMeans will be used for the statistical comparison; the 95% CI will be reported.

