6.3. Adjustments for Covariates

The randomization at the beginning of Open-Label Treatment Period (Period 2) is stratified by concomitant csDMARD use at baseline (Yes, No) and moderate-to-severe plaque psoriasis involvement (Yes, No). Unless otherwise specified, all efficacy and health outcome analyses during Period 2 will include the concomitant csDMARD use at baseline and moderate-to-severe plaque psoriasis involvement in the model. In general, when an MMRM is to be used for analyses, baseline value and baseline-by-visit interactions will be included as covariates; when an ANCOVA is to be used for analyses, baseline value will be included as a covariate.

The OBSMARGINS/OM option will be used in the LSMEANS statement in SAS to account for imbalance in the stratification variables.

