Coates criteria for Minimal Disease Activity (MDA) (6 enthesal points)	Proportion of patients achieving MDA (6 enthesal points)	Logistic regression using the NRI method (see Section 6.4.1)	ITT population	IXE vs ADA at each post-baseline visit	Secondary analysis
		Fisher's exact test using the NRI method (see Section 6.4.1)	ITT population	IXE vs ADA at each post-baseline visit	Secondary analysis
Coates criteria for Minimal Disease Activity (MDA) (18 enthesal points)	Proportion of patients achieving Coates criteria for MDA (18 enthesal points)	Logistic regression using the NRI method (see Section 6.4.1)	ITT population	IXE vs ADA at each post-baseline visit	Secondary analysis
		Fisher's exact test using the NRI method (see Section 6.4.1)	ITT population	IXE vs ADA at each post-baseline visit	Secondary analysis

Measure	Variable	Analysis Method (Section 6.2)	Population (Section 6.1.3)	Comparison/Time Point	Analysis Type
Leeds Enthesitis Index (LEI)	
 Change from baseline in LEI score 	MMRM	ITT population - patients with baseline enthesitis (LEI >0)	IXE vs ADA at each post-baseline visit	Secondary analysis
		ANCOVA model using mBOCF (see Section 6.4.2)	ITT population - patients with baseline enthesitis (LEI >0)	IXE vs ADA at each post-baseline visit	Secondary analysis
	Proportion of patients with complete resolution in enthesitis (LEI score = 0)	Logistic regression using the NRI method (see Section 6.4.1)	ITT population - patients with baseline enthesitis (LEI >0)	IXE vs ADA at each post-baseline visit	Secondary analysis
		Fisher's exact test using the NRI method (see Section 6.4.1)	ITT population for patients with baseline enthesitis (LEI >0)	IXE vs ADA at each post-baseline visit	Secondary analysis
Leeds Dactylitis Index-Basic (LDI-B)	
 Change from baseline in LDI-B score 	MMRM	ITT population - patients with baseline dactylitis (LDI-B >0)	IXE vs ADA at or after Week 12	Secondary analysis
		ANCOVA model using mBOCF (see Section 6.4.2)	ITT population - patients with baseline dactylitis (LDI-B >0)	IXE vs ADA at or after Week 12	Secondary analysis
	Proportion of patients with complete resolution in dactylitis (LDI-B score = 0)	Logistic regression using the NRI method (see Section 6.4.1)	ITT population - patients with baseline dactylitis (LDI-B >0)	IXE vs ADA at or after Week 12	Secondary analysis

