		ANCOVA model using mBOCF (see Section 6.4.2)	ITT population - patients with baseline fingernail involvement (NAPSI >0)	IXE vs ADA at or after Week 12	Secondary analysis
	Proportion of patients with complete resolution in nail psoriasis (NAPSI = 0)	Logistic regression using the NRI method (see Section 6.4.1)	ITT population - patients with baseline fingernail involvement (NAPSI >0)	IXE vs ADA at each post-baseline visit at or after Week 12	Exploratory analysis
		Fisher’s exact test using the NRI method (see Section 6.4.1)	ITT population - patients with baseline fingernail involvement (NAPSI >0)	IXE vs ADA at each post-baseline visit at or after Week 12	Exploratory analysis

Abbreviations: ADA = adalimumab; ANCOVA = analysis of covariance; ITT = intent to treat; IXE = ixekizumab; mBOCF = modified baseline observation carried forward; MMRM = mixed-effects model of repeated measures; NRI = non-responder imputation.

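### The logistic models for complete resolution (LEI, SPARCC, LDI-B, NAPSI and Itch NRS = 0) leave out the baseline score, which gives up some power and leaves chance imbalance in starting severity uncorrected; minor

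*SAP*

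**What the plan says.** SAP 6.2.1 sets the primary method for binary efficacy and health outcome variables as "a logistic regression model with treatment, concomitant csDMARD use at baseline, and moderate-to-severe plaque psoriasis involvement as factors", with odds ratios and 95% confidence intervals. Fisher's exact test is the secondary method. Protocol 10.3.3.1.1 specifies the same logistic model. SAP 6.2.1 also reports treatment differences, relative risks and NNT with normal-approximation intervals, and Appendix 1 builds NNT from the difference in response rates.

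Table RHCF.6.4 applies this model to "Proportion of patients with complete resolution in enthesitis (LEI score = 0", to the matching SPARCC and LDI-B variables, and to "Proportion of patients with complete resolution in nail psoriasis (NAPSI = 0". Table RHCF.6.6 applies it to Itch NRS = 0. All five use nonresponder imputation in ITT patients whose baseline score on that measure is above zero.

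For the continuous form of these measures, SAP 6.2.2 includes "baseline value as covariate and baseline-by-visit and treatment-by-visit interaction terms". SAP 6.3 states the general rule for MMRM and adds that "when an ANCOVA is to be used for analyses, baseline value will be included as a covariate". It names the baseline value for no other model. SAP 5.3 gives the factors used at randomisation: "The randomization will be stratified by concomitant csDMARD use at baseline (Yes, No) and moderate-to-severe plaque psoriasis involvement (Yes, No".

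**The concern.** Whether a patient reaches zero plausibly depends on the starting score. Within these subsets LEI can start anywhere from 1 to 6, SPARCC from 1 to 16 and fingernail NAPSI from 1 to 80. Neither stratification factor measures this: one is csDMARD use, and the other is plaque psoriasis severity defined by PASI, sPGA and BSA. A prognostic variable that is complete in the analysis set is therefore left out of the binary models, although the plan uses it for the continuous version of the same measure.

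Two things are at stake. A prognostic covariate usually adds power in a logistic model. And if the arms happen to differ in starting severity, the unadjusted comparison carries that difference into the result. SAP 6.9.1 will tabulate and test the baseline scores between arms, but the plan names no adjusted binary analysis to turn to if they differ, so any later adjustment would be post hoc.

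**Working it through.** **The plan's own figures.** SAP 5.2 states power for three tests at 275 per arm and none for a resolution endpoint. The three figures reproduce within 2 points:

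- ACR50 noninferiority: SE = sqrt[(0.438×0.562 + 0.441×0.559)/275] = 0.0423. Power = Φ[(0.12 − 0.003)/0.0423 − 1.96] = Φ(0.80) = 78.9% (stated 78%).
- Primary endpoint, 31.3% vs 13.6%: 99.9% by normal approximation and 99.87% by exact enumeration of Fisher's test (stated approximately 99%).
- PASI 100, 46.9% vs 23.7%: above 99.9% (stated approximately 99%).

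**Inputs for the resolution endpoints.** The documents give no subset sizes, no adalimumab resolution rates and no measure of how strongly the baseline score predicts resolution. The only ixekizumab figures are for LDI-B = 0 at Week 24 in Study RHAP (80% and 77%, Protocol 3.2). The following are therefore assumptions: 50 or 150 patients per arm, 50% control resolution, a conditional treatment odds ratio of 2.0 (or 1.0 under the null), a normally distributed baseline score with an odds ratio per SD of 1.0 to 3.0, and stratification factors without effect on the outcome.

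**Power.** In 3,000 simulated trials per case, the SAP model was compared with the same model plus the baseline score (Wald test, two-sided 5%):

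| Baseline OR per SD | 150/arm: without → with | 50/arm: without → with |
|---|---|---|
| 1.0 | 82.2% → 82.1% | 41.1% → 40.0% |
| 1.5 | 80.8% → 82.3% | 38.2% → 39.4% |
| 2.0 | 75.2% → 78.7% | 33.1% → 35.5% |
| 3.0 | 65.7% → 75.0% | 27.5% → 32.7% |

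Unadjusted power falls down the columns because the conditional odds ratio is held at 2.0, so the marginal treatment rate drops from 66.7% to 63.6%.

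A second simulation (2,000 trials per case) fixed the marginal rates by measure, again by assumption:

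- LEI = 0, 160/arm, 50% vs 64.5%: 75–76% without baseline, 77–80% with it.
- NAPSI = 0, 180/arm, 40% vs 54.5%: 79% and 80–86%.
- LDI-B = 0, 45/arm: about 80% and 80–84%.
- Itch NRS = 0: gain under 1 point.

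**Standard error.** At 150/arm and treatment OR 2.0, the mean SE of the log odds ratio rises with adjustment: 0.239 to 0.254 (OR per SD 2.0) and 0.238 to 0.269 (3.0). The mean log odds ratio rises by more, from 0.635 to 0.704 and from 0.569 to 0.712. The ratio of estimate to SE therefore goes from 2.66 to 2.77 and from 2.39 to 2.65. The variance of a standardised risk difference falls by about 0%, 4%, 10% and 19% across the four prognostic strengths.

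**Chance imbalance.** One SE of imbalance in the mean score is sqrt(2/n) SD: 0.115 at 150/arm and 0.20 at 50/arm. To first order the unadjusted difference shifts by p(1−p) × |ln OR per SD| × imbalance. At 150/arm and p = 0.5:

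- OR per SD 1.5: 0.25×0.405×0.1155 = 1.2 points.
- OR per SD 2.0: 0.25×0.693×0.1155 = 2.0 points.
- OR per SD 3.0: 0.25×1.099×0.1155 = 3.2 points.

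The SE of the difference is sqrt(2×0.25/150) = 5.8 points, so a 1-SE imbalance is worth about 20% to 55% of it.

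**Type I error.** Without the baseline score, overall rejection of a true null was 4.2% to 5.6% across cases. In the 10% of trials with the largest imbalance (150/arm), it was 8.7% unadjusted against 5.0% adjusted at OR per SD 2.0, and 13.3% against 4.0% at 3.0. Each of these rests on about 300 trials, so the Monte Carlo SE near 5% is sqrt(0.05×0.95/300) = 1.3 points.

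**The case against.** The strongest reply is that this is a consistent, prespecified choice. Protocol and SAP give the same logistic model for every binary endpoint, and other threshold endpoints (absolute PASI, MDA, mCPDAI ≤5, DLQI 0/1) are treated alike. Baseline imbalance will be visible in the SAP 6.9.1 tables. Adjusted MMRM and ANCOVA are already planned for each measure, in the same subsets for LEI, SPARCC, LDI-B and NAPSI and in the full ITT set for Itch NRS. The size of any gain rests on assumed inputs. All of this stands, and it limits the point to a cheap improvement.

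Four stronger readings are tempting, and the documents do not support them:

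- A reader might infer that the reported odds ratio loses precision. It does not: adjustment raises the SE of the log odds ratio. What is given up is power, and precision of a standardised risk difference.
- A reader might infer that randomisation fails to balance the score in these subsets. A subset defined by a baseline value keeps the randomised comparison and is balanced in expectation. The confidence interval already covers ordinary chance imbalance; the concern is conditional on the imbalance observed.
- A reader might see a contradiction between SAP 6.2.1 and 6.2.2. There is none: each states its own model.
- A reader might blame any disagreement between MMRM and logistic results on baseline adjustment alone. The two also differ in outcome (change against reaching zero) and in missing-data handling (likelihood-based against nonresponder imputation).

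**Conclusion.** The point holds as a minor one. The five resolution models omit a baseline score that is known for every patient analysed and is used elsewhere in the plan for the same measures. Under the assumptions above the cost is about 0 to 9 percentage points of power. It is nil if the score is not prognostic (adjustment then cost about 1 point at 50/arm), and a simulation put it under 1 point for Itch NRS. The simulations give the adjusted model the correct functional form, so real gains with discrete or skewed scores could be smaller. Overall type I error is near nominal; only in trials with a large imbalance is the unadjusted test misleading.

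The endpoints are secondary, NAPSI = 0 is exploratory, and all lie outside the testing sequence in SAP 6.6. No primary or major secondary conclusion depends on this.

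**What to change.** In SAP 6.2.1, 6.3 and Tables RHCF.6.4 and 6.6, add the baseline value of the same measure as a continuous covariate to the logistic models for LEI, SPARCC, LDI-B, NAPSI and Itch NRS = 0, and keep the two stratification factors. Use the log scale for LDI-B and NAPSI; every score in these subsets is above zero, so the log is defined. If data are already locked, run this as a labelled sensitivity analysis.

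State that the odds ratio is then conditional on baseline score. Derive a standardised risk difference from the adjusted model; without this step the treatment differences, relative risks and NNT in SAP 6.2.1 and Appendix 1 would stay unadjusted. Keep Fisher's exact test as the unadjusted check.

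The cost is one model term, a standardisation step and a few sentences of SAP text. No new data are needed and no patient is lost. The downside is an odds ratio conditional on one more covariate than for the other binary endpoints, with a slightly larger SE on the log scale.

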6.12.1. Analysis Methodology for Primary and Major Secondary Outcomes

6.12.1.1. Primary Outcome and Methodology

The primary efficacy endpoint is the proportion of patients simultaneously achieving both ACR50 and PASI 100 responses at Week 24.

ACR50 response is an efficacy measure for which a patient must satisfy the following:

1. $\geq 50\%$ improvement from baseline in TJC and
2. $\geq 50\%$ improvement from baseline in SJC and
3. $\geq 50\%$ improvement from baseline in at least 3 of the following 5 ACR Core Set criteria:
 - a. Patient's Assessment of Pain Visual Analog Scale (VAS)
 - b. PatGA VAS
 - c. PGA VAS
 - d. patient's assessment of physical function as measured by the HAQ-DI
 - e. acute-phase reactant as measured by high sensitivity (assay) CRP (hs-CRP)

Full details of the algorithm to calculate ACR Response can be found in [Appendix 2](#).

PASI 100 is an efficacy measure for which a patient must meet an improvement of 100% in the PASI compared to baseline.

The primary analysis for comparison of ixekizumab with adalimumab at Week 24 using the primary efficacy endpoint will be a logistic regression analysis as described in Section [6.2.1](#) based on the ITT population in the Open-Label Treatment Period (Period 2). Missing data will be imputed using the NRI method described in Section [6.4.1](#).

6.12.1.2. Methodology for Major Secondary Outcomes

The major secondary endpoints are as follows:

1. Proportion of patients achieving ACR50 in each treatment group at Week 24
2. Proportion of patients achieving PASI 100 in each treatment group at Week 24

The analyses of the secondary endpoints will be based on the ITT population in the Open-Label Treatment Period (Period 2) comparing ixekizumab versus adalimumab at Week 24 using methods described in Section [6.7](#) for the major secondary endpoint #1 and using methods from Section [6.2.1](#) for the major secondary endpoint #2. Missing data will be imputed using the NRI method described in Section [6.4.1](#).

A multiple testing procedure, as described in Section [6.6](#), will be used for testing the primary and major secondary endpoints.

6.12.1.3. Other Secondary Outcomes

There will be no adjustment for multiple comparisons for other secondary analyses. The secondary analyses are detailed in [Table RHCF.6.3](#) and [Table RHCF.6.4](#).

By-patient listings for primary efficacy measurements ACR and PASI will be provided.

6.13. Health Outcomes/Quality-of-Life Analyses

The health outcomes and quality of life (QOL) measures are Itch NRS, Fatigue Severity NRS, SF-36, EQ-5D-5L, DLQI, and Treatment Satisfaction Questionnaire. [Table RHCF.6.5](#) includes the description and derivation of the health outcomes and QOL measures.

The analyses of health outcome variables for Period 2 will be based on the ITT population.

[Table RHCF.6.6](#) provides the detailed analyses including analysis type, method and imputation, population, time point, and treatment group comparisons for health outcomes and QOL analyses.

Table RHCF.6.5. Description and Derivation of Health Outcomes and Quality-of-Life Measures

Measure	Description	Variable	Derivation/Comment	Imputation Approach if with Missing Components
Itch Numeric Rating Scale (NRS)	A single-item, patient-reported outcome (PRO) measure designed to capture information on the overall severity of a patient’s itching due to their psoriatic skin condition by having the patient selecting the integer that best describes the worst level of itching in the past 24 hours on an 11-point NRS anchored at 0 representing “no itching” and 10 representing “worst itch imaginable.”	
 Itch NRS score 	Range from 0 to 10	Single item, missing if missing
		
 Change from baseline in Itch NRS score 	Calculated as: observe Itch NRS score – baseline Itch NRS score	Missing is baseline or observed value is missing
		
 Itch NRS=0 	Defined as a post-baseline Itch NRS score of 0	Missing if Itch NRS score is missing
Fatigue Severity Numeric Rating Scale (NRS)	A patient-administered single-item 11-point horizontal scale anchored at 0 and 10, on which 0 represents “no fatigue” and 10 represents “as bad as you can imagine.” Patients rate their fatigue (feeling tired or worn out) by selecting the single number that describes their worst level of fatigue during the past 24 hours.	
 Fatigue Severity NRS 	Range from 0 to 10.	Single item, missing if missing
		
 Change from baseline in Fatigue severity NRS 	Calculated as: observe Fatigue NRS score – baseline Fatigue NRS score	Missing is baseline or observed value is missing
Medical Outcomes Study 36-item Short Form Health Survey (SF-36)	A 36-item patient-administered measure designed to be a short, multipurpose assessment of health in the areas of physical functioning, role-physical, role-emotional, bodily pain, vitality, social functioning, mental health, and general health. The 2 overarching domains of mental well-being and physical well-being are captured by the Mental Component Summary (MCS) and Physical Component Summary (PCS) scores.	Observed and change from baseline in: 8 associated domain scores: 
 Physical Functioning Role Physical Bodily Pain General Health Vitality Social Functioning Role Emotional Mental Health 	Per copyright owner, the Quality Metric Health Outcomes™ Scoring Software 4.5 will be used to derive SF-36 domain and component scores. After data quality-controls, the SF-36 software will re-calibrate the item-level responses for calculation of the domain and component scores. These raw scores will be transformed into the domain scores (t-scores)	Missing data handling offered by SF-36 software will not be used

Measure	Description	Variable	Derivation/Comment	Imputation Approach if with Missing Components
	
Items are answered on Likert scales of varying lengths. The SF-36 version 2 (acute version) health survey will be used, which has a 1-week recall period (Brazier et al. 1992; Ware and Sherbourne 1992).
	
2 component Scores:
 
 • MCS Score • PCS Score 	
using the 1-week recall period. The procedure to derive the SF-36 scores is described in Appendix 6. The summary scores range from 0 to 100. It entails exporting the patient data in a CSV or tab-delimited file for import, generation of the SF-36 scores and reports, and export of the calculated scores in a CSV or tab-delimited file for integration into SDTM/ADaM datasets. The summary scores range from 0 to 100.
	

Measure	Description	Variable	Derivation/Comment	Imputation Approach if with Missing Components

European Quality of Life - 5 Dimensions - 5 Level (EQ-5D-5L)
	
The EQ-5D-5L is a standardized measure of health status used to provide a simple, generic measure of health for clinical and economic appraisal. The EQ-5D-5L consists of 2 components: a descriptive system of the respondent’s health and a rating of his or her current health state using a 0- to 100-mm VAS.
 
The descriptive system comprises the following 5 dimensions: item 1: mobility item 2: self-care item 3: usual activities item 4: pain/discomfort item 5: anxiety/depression
 
The respondent is asked to indicate his or her health state by ticking (or placing a cross) in the box associated with the most appropriate statement in each of the 5 dimensions.
 
The EQ-5D-5L health states, defined by the EQ-5D-5L descriptive system, may be converted into a single summary index by applying a formula that essentially attaches values (also called weights) to each of the levels in each dimension (EuroQol Group [WWW]).
 
The VAS records the respondent’s self-rated health on a vertical VAS where the endpoints are labeled 100 = “best imaginable health state” and 0 = “worst imaginable health state.” This information can be used as a quantitative measure of health
	
 • EQ-5D mobility, • EQ-5D self-care, • EQ-5D usual activities, • EQ-5D pain/discomfort, • EQ-5D anxiety/depression, 	
5 health profile dimensions, each dimension has 5 levels: 1 = no problems 2 = slight problems 3 = moderate problems 4 = severe problems 5 = extreme problems
 
It should be noted that the numerals 1 to 5 have no arithmetic properties and should not be used as a primary score.
	
Each dimension is a single item, missing if missing. (Note: Score of 9 is missing.)

Measure	Description	Variable	Derivation/Comment	Imputation Approach if with Missing Components
		EQ-5D VAS	Range from 0 = “worst imaginable health state” to 100 = “best imaginable health state”. Note: higher value indicates better health state.	Single item, missing if missing
		EQ-5D-5L UK Population-based index score	Uses the concatenation of the value of each EQ- 5D-5L dimension score in the order: item1; item2; item3; item4; item5. Derive EQ-5D-5L UK Population-based index score according to the link by using the UK algorithm (Szende et al. 2007) to produce a patient-level index score between -0.59 and 1.0 (continuous variable): http://www.euroqol.org/fileadmin/user_upload/Documenten/Excel/Crosswalk_5L/EQ-5D-5L_Crosswalk_Value_Sets.xls	If any of the items is missing or equal to 9, the index score is missing

Measure	Description	Variable	Derivation/Comment	Imputation Approach if with Missing Components
Dermatology Life Quality Index (DLQI)	
The DLQI is a validated, dermatology-specific, patient-reported measure that evaluates patient’s health-related quality of life. This questionnaire has 10 items that are grouped in 6 domains, including symptoms and feelings, daily activities, leisure, work and school, personal relationships, and treatment. The recall period of this scale is over the “last week.”
 
Response categories and corresponding scores are:
 
 Very much = 3 A lot = 2 A little = 1 Not at all = 0 Not relevant = 0 	DLQI symptoms and feelings domain	
Sum of responses of questions #1 and #2:
 
 #1. How itchy, sore, painful or stinging has your skin been? #2. How embarrassed or self-conscious have you been because of your skin? 	If 1 question in a domain is missing, that domain is missing.

Measure	Description	Variable	Derivation/Comment	Imputation Approach if with Missing Components
		DLQI daily activities domain	Sum of responses of questions #3 and #4: #3. How much has your skin interfered with you going shopping or looking after your home or garden? #4. How much has your skin influenced the clothes you wear?	If 1 question in a domain is missing, that domain is missing.
		DLQI leisure domain	Sum of responses of questions #5 and #6: #5. How much has your skin affected any social or leisure activities? #6. How much has your skin made it difficult for you to do any sport?	If 1 question in a domain is missing, that domain is missing.
		DLQI work and school domain	Sum of responses of questions #7A and #7B: #7A. Has your skin prevented you from working or studying? #7B. If No: how much has your skin been a problem at work or studying?	If the answer to question #7A is missing, this domain is missing. If #7A is No, and #7B is missing, this domain is missing.
		DLQI personal and relationships domain	Sum of responses of questions #8 and #9: #8. How much has your skin created problems with your partner or any of your close friends or relatives? #9. How much has your skin caused any sexual difficulties?	If 1 question in a domain is missing, that domain is missing.
		DLQI treatment	Response of question #10: #10. How much of a problem	If 1 question in a domain is missing, that domain is

Measure	Description	Variable	Derivation/Comment	Imputation Approach if with Missing Components
			has the treatment for your skin been, for example by making your home messy, or by taking up time?	missing.
		DLQI total score	A DLQI total score is calculated by summing all 10 question responses and has a range of 0 to 30 (less to more impairment) (Finlay and Khan 1994; Basra et al. 2008).	If 2 or more questions are missing, the total score is missing. Note: #7B could be a valid missing while #7A is not “No.” That is, #7 should be considered as 1 question.
		Change from baseline in DLQI total score	Calculated as observed DLQI – baseline DLQI	Missing if baseline or observed value are missing
		DLQI (0,1)	A DLQI (0,1) response is defined as a post-baseline DLQI total score of 0 or 1. A DLQI total score of 0 to 1 is considered as having no effect on a patient’s HRQoL (Khilji et al. 2002; Hongbo et al. 2005).	Missing if DLQI total score is missing
Treatment Satisfaction Questionnaire (TSQ)	The TSQ is a clinician-administered questionnaire that provides an assessment of the patient’s opinion of the effectiveness, safety, and overall satisfaction of the study medication. Patients will be asked to respond to questionnaire items using a 4-point	Question #1 = “mostly satisfied”	Patient’s answer to Question #1: Please tell me whether you are mostly satisfied, somewhat satisfied, somewhat dissatisfied, or mostly dissatisfied with the effectiveness of this medication is mostly satisfied.	Single item, missing if missing

Measure	Description	Variable	Derivation/Comment	Imputation Approach if with Missing Components
		Question #2 = “mostly satisfied”	Patient’s answer to Question #2: Please tell me whether you are mostly satisfied, somewhat satisfied, somewhat dissatisfied, or mostly dissatisfied with the effectiveness over time of this medication is mostly satisfied.	Single item, missing if missing
		Question #3 = “mostly satisfied”	Patient’s answer to Question #3: Please tell me whether you are mostly satisfied, somewhat satisfied, somewhat dissatisfied, or mostly dissatisfied with the long term safety of this medication is mostly satisfied.	Single item, missing if missing
		Question #4 = “mostly satisfied”	Patient’s answer to Question #4: How would you rate your overall satisfaction with this medication is mostly satisfied.	Single item, missing if missing

Table RHCF.6.6. Description of Health Outcomes and Quality-of-Life Analyses

Measure	Variable	Analysis Method (Section 6.2)	Population (Section 6.1.3)	Comparison/Time Point	Analysis Type
Itch NRS	
 Change in baseline for Itch NRS 	MMRM	ITT population	At each post-baseline visit	Secondary analysis
		ANCOVA model using mBOCF (see Section 6.4.2)	ITT population	At each post-baseline visit	Secondary analysis
	Itch NRS = 0	Logistic regression using the NRI method (see Section 6.4.1)	ITT population for patients with baseline Itch NRS >0	At each post-baseline visit	Secondary analysis
		Fisher’s exact test using the NRI method (see Section 6.4.1)	ITT population for patients with baseline Itch NRS >0	At each post-baseline visit	Secondary analysis
Fatigue Severity NRS	
 Change from baseline in fatigue severity NRS score 	MMRM	ITT population	At Week 4, 12, 16, 24, 32, and 52	Secondary analysis
		ANCOVA model using mBOCF (see Section 6.4.2)	ITT population	At Week 4, 12, 16, 24, 32, and 52	Secondary analysis
Medical Outcomes Study 36-item Short-Form Health Survey	Change from baseline in: 
 Mental component summary score Physical component summary score 	MMRM	ITT population	At Week 4, 12, 16, 24, 32, and 52	Secondary analysis
		ANCOVA model using mBOCF (see Section 6.4.2)	ITT population	At Week 4, 12, 16, 24, 32, and 52	Secondary analysis
	Change from baseline in 8 domain scores	MMRM	ITT population	At Week 4, 12, 16, 24, 32, and 52	Exploratory analysis
		ANCOVA model using mBOCF (see Section 6.4.2)	ITT population	At Week 4, 12, 16, 24, 32, and 52	Exploratory analysis

Measure	Variable	Analysis Method (Section 6.2)	Population (Section 6.1.3)	Comparison/Time Point	Analysis Type
DLQI	
 Change from baseline in DLQI total score 	MMRM	ITT population	At each post-baseline visit	Secondary analysis
		ANCOVA model using mBOCF (see Section 6.4.2)	ITT population	At each post-baseline visit	Secondary analysis
	
 DLQI (0,1) 	Logistic regression using the NRI method (see Section 6.4.1)	ITT population	At each post-baseline visit	Exploratory analysis
		Fisher’s exact test using the NRI method (see Section 6.4.1)	ITT population	At each post-baseline visit	Exploratory analysis
EQ-5D-5L	
 Change from baseline in EQ-5D VAS 	MMRM	ITT Population	At Week 4, 12, 16, 24, 32, and 52	Secondary analysis
		ANCOVA model using mBOCF (see Section 6.4.2)	ITT Population	At Week 4, 12, 16, 24, 32, and 52	Secondary analysis
	Change from baseline in EQ-5D-5L UK Population-based index score	MMRM	ITT Population	At Week 4, 12, 16, 24, 32, and 52	Secondary analysis
		ANCOVA model using mBOCF (see Section 6.4.2)	ITT Population	At Week 4, 12, 16, 24, 32, and 52	Secondary analysis
TSQ	Proportion of patients answering “mostly satisfied” to 
 Question #1 Question #2 Question #3 Question #4 	Logistic regression using the NRI method (see Section 6.4.1)	ITT population	At Week 12, 24, and 52	Secondary analysis
		Fisher’s exact test using the NRI method (see Section 6.4.1)	ITT population	At Week 12, 24, and 52	Secondary analysis

Abbreviations: ANCOVA = analysis of covariance; EQ-5D-5L = European Quality of Life-5 Dimensions 5 Level Health Outcomes Instrument; DLQI = Dermatology Life Quality Index; ITT = intent-to-treat; mBOCF = modified baseline observation carried forward; MMRM = mixed-effects model of repeated measures; NRI = non-responder imputation; NRS = Numeric Rating Scale; TSQ = Treatment Satisfaction Questionnaire; UK = United Kingdom; VAS = Visual Analog Scale.

